Cognitive Recovery With Cannabis Abstinence Among
High School-Aged Adolescents

NCT03276221

Document Date: 04/28/2023

Cognitive Recovery with Cannabis Abstinence Among High-school-aged Adolescents

Statistical Analysis Plan

The ARCHES Team

NCT: 03276221

First created 2/12/2022

Last revised 04/28/2023

Unblinded analysis 02/03/2023

Version 2.2

Table of Contents

Study Design	4
Participants	4
Order of data collection and creation of the analysis plan	5
Analyst-blind	5
Primary Outcomes.....	7
CANTAB tasks	7
Selection of outcomes.....	10
Statistical model.....	15
Key confirmatory effect.....	16
Multiple comparisons.....	16
Covariates	16
Missing data	17
Clinical Significance	17
Secondary analyses	18
Secondary Outcomes	20
CANTAB tasks	20
Selection of outcomes.....	20
Statistical model.....	21
Power	22
Software	24
References	25

Study Design

The study consisted of a one-month (with a two-month follow-up) longitudinal trial of cannabis abstinence (with data collection from 9/2017 to 12/2022) designed to determine:

1. Whether cognitive performance improves for students abstinent from cannabis use for one month above and beyond any improvement observed for students engaging in continued use.
2. When cognitive performance improves (if improvement during abstinence does occur).
3. Whether cognitive performance in abstinent individuals "returns" to performance levels observed in non-using peers.

Participants

The study planned to recruit 210 adolescents across the following conditions:

1. A control group of non-cannabis users (Non-users; n = 70).
2. Regular users of cannabis (n = 140) randomized to either...
 - a. Contingency management intervention that incentivized 4 weeks of cannabis abstinence (CB-Abst; n = 70).
 - b. Non-contingent monitoring with no abstinence requirement (CB-Mon; n = 70).

All participants completed cognitive assessments, toxicology testing, self-report questionnaires and semi-structured mood and substance use interviews during the 4-week study as well as one 30-day follow-up visit. Abstinence was verified using the statistical model of Schwilke and colleagues (2011). The approach differentiates residual cannabinoid excretion from new cannabis exposure by comparing observed urine metabolite ratios against expected ratios. Observed ratios that exceed a 95% confidence interval indicate new cannabis use.

Order of data collection and creation of the analysis plan

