The 16 primary outcomes for the study were measures taken from 7 modules provided by the Cambridge Neuropsychological Test Automated Battery (CANTAB; Cambridge Cognition, 2019). The set of modules used for assessing each domain of interest (memory and executive functioning, respectively) were determined via CANTAB's recommendations listed on their website (see <https://www.cambridgecognition.com/cantab/cognitive-tests/memory/> for modules to assess memory and <https://www.cambridgecognition.com/cantab/cognitive-tests/memory/> for modules to assess executive functioning). Note subjects completed one additional module (the Motor Screening Task; MOT) at the start of each session, but since this module was intended primarily for calibration and training, we exclude it from analyses. We also note that while often researchers will collapse multiple outcomes into a smaller set of composite scores for interpretability and to avoid issues with multiple comparisons, it is difficult to do so with the CANTAB modules due a complex hierarchical correlation structure across tasks and domains of interest (e.g., Lenehan, Summers, Saunders, Summers, & Vickers, 2015). However, as an exploratory analysis we do include a replication of the method used for a pilot study of the current project ([name] et al., 2018) in which a smaller set of CANTAB modules (which partially overlap with those assessed for the current study) was analyzed.

CANTAB tasks

The 3 modules for assessment of memory were...

1. The Paired Associates Learning (PAL) module.

Description: Subjects were shown a set of boxes. The boxes were opened in random order to display a symbol hidden in the box. Symbols were then shown in the center of the screen. The goal of the task was to select the box that the onscreen symbol was originally hidden in. There were 20 trials in total, 4 trials each for conditions with 2, 4, 6, 8, and 12 boxes onscreen.

2. The Spatial Span (SSP) module.

Description: Subjects were shown a set of white squares, each of which briefly change color in a set order. The goal of the task was then to select the boxes that changed color either (a) in the order that they changed color (the forward variant), or (b) in the reverse of the order that they changed color (the backward variant). Each variant consisted of 8 trials, starting with 2 boxes and ending at 9 boxes on screen.

3. The Verbal Recognition Memory (VRM) module.

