Continuous outcomes (e.g., latencies and reaction times) were fit using a standard linear regression model. Bounded count outcomes (e.g., number of errors or correct responses) were fit using binomial regression. Specifically, let $y_{(p,t)}$ refer to the outcome value for participant p at time t , where $y_{(p,t)} = \{0, 1, \dots, H\}$ with H referring to the highest possible value. We assumed that $y_{(p,t)}$ was distributed according to a binomial process governed by a latent probability $\theta_{(p,t)}$:

$$y_{(p,t)} \sim \text{Binomial}(\theta_{(p,t)}).$$

The log-odds of this latent probability can then be decomposed into the weighted sum of the predictors of interest.

In contrast to linear regression, which includes a parameter for the residual standard deviation, binomial regression has no additional parameter to handle overdispersion. While failure to account for overdispersion can lead to underestimation of standard errors, as noted before the GEE approach is robust to misspecification of distributional assumptions and corrects for this underestimation, and as such we did not need to implement any additional steps to address overdispersion issues.

Key confirmatory effect

The key confirmatory effect of interest for each outcome will be a dummy-coded contrast between CB-Mon (the referent, coded as 0) and CB-Abst (coded as 1), testing whether a constant effect of abstinence exists, averaged over all time points.

Multiple comparisons

Each module/task from the CANTAB examines a separate cognitive process of interest. We therefore address multiple comparisons issues within each module. As the number of outcomes per module range from 1 to 4, we used a simple Bonferroni correction, dividing the desired error rate of 5% by the number of outcomes per module. Therefore, effects of interest were flagged as statistically significant for $\alpha = 0.05$ (for the SST module), $\alpha = 0.025$ (for the PAL, SSP, OTS, and SWM modules), $\alpha = 0.0167$ (for the VRM module), and $\alpha = 0.0125$ (for the MTT module).

Covariates

The covariates we included for the primary analysis were:

- A coefficient for a linear trend to capture change over time, coded as week 1 = -3, week 2 = -1, week 3 = 1, and week 4 = 3.
- A subject's baseline value for a given outcome, converted to a z-score.

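### Error is controlled only within CANTAB modules (VRM not even to 5%), so one flagged module should not answer research question 1; within modules, Holm dominates the single-step Bonferroni

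*SAP*

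**What the plan says.** Under Study Design, the SAP's first research question is "Whether cognitive performance improves for students abstinent from cannabis use for one month above and beyond any improvement observed" in continuing users. Under Key confirmatory effect, every outcome gets a contrast of CB-Abst against CB-Mon, "testing whether a constant effect of abstinence exists, averaged over all time points", with no direction specified.

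Under Multiple comparisons, the family is the module: "Each module/task from the CANTAB examines a separate cognitive process of interest. We therefore address multiple comparisons issues within each module". The method is single-step: "we used a simple Bonferroni correction, dividing the desired error rate of 5% by the number of outcomes per module". The stated levels are 0.05 (SST), 0.025 (PAL, SSP, OTS, SWM), 0.0167 (VRM) and 0.0125 (MTT). There is no ranked primary outcome, no step across modules and no overall error rate.

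Primary Outcomes opens with 16 outcomes. Selection of outcomes lists 17: PAL 2, SSP 2, VRM 4, MTT 4, OTS 2, SST 1, SWM 2. The Analyst-blind section says that the fourth VRM outcome, immediate free recall, was added after the first unblinded analyses. The front page dates the unblinded analysis 02/03/2023.

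Primary Outcomes notes that composites are often used to limit multiplicity, but declines them because of a "complex hierarchical correlation structure across tasks and domains of interest". The Power section plans 80% power at two-sided 0.05, unadjusted.

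**The concern.** Seventeen contrasts, all called confirmatory, feed one research question, and each module is a separate chance to flag something. The plan does not say what pattern of flags would answer the question. It gives up composites, the usual way to reduce the number of tests, and puts nothing in their place across modules. A report could therefore present one flagged module as confirmatory evidence that abstinence improves cognition, at an error rate that the plan never states.

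A second, separable matter is efficiency. Within a module, single-step Bonferroni holds the familywise rate at 5%, but Holm holds the same bound with no added assumption and never rejects fewer hypotheses. Real effects on the second and later outcomes of a module can be missed for no gain in protection.

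**Working it through.** **1. The plan's own levels.** Formula: 0.05 divided by the number of outcomes in the module.

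- SST 0.05/1 = 0.05; PAL, SSP, OTS, SWM 0.05/2 = 0.025; MTT 0.05/4 = 0.0125. These six agree with the SAP.
- VRM: items 1.5 to 1.8 are four outcomes, so 0.05/4 = 0.0125. The SAP's 0.0167 is 0.05/3. As written, the bound for VRM is 4 × 0.0167 = 6.7%, or 1 − (1 − 0.0167)^4 = 6.5% if its outcomes are independent.

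**2. Chance of at least one false flag, no true effects, independent outcomes.**

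- As written: 1 − (0.975^8 × 0.9833^4 × 0.9875^4 × 0.95) = 1 − (0.8167 × 0.9349 × 0.9509 × 0.95) = 31.0%.
- With VRM at 0.0125: 1 − (0.8167 × 0.9509 × 0.9509 × 0.95) = 29.9%.
- Toward improvement only (each level halved, as written): 16.8%.

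**3. The same with correlation.** The SAP gives no correlations, so these are assumptions. Test statistics were simulated as normal (400,000 draws) at the SAP's levels, with outcomes oriented so that positive means better.

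| Correlation within / between modules | Either direction | Toward improvement |
|---|---|---|
| 0 / 0 | 31.0% | 16.8% |
| 0.3 / 0.1 | 29.9% | 15.5% |
| 0.5 / 0.1 | 28.5% | 14.8% |
| 0.5 / 0.3 | 25.4% | 12.8% |
| 0.5 / 0.5 | 20.5% | 10.3% |
| 0.7 / 0.5 | 19.6% | 9.8% |
| 0.8 / 0.6 | 16.5% | 8.2% |

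The two RVP secondary outcomes are not counted.

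**4. Holm against Bonferroni within a module.** Each real effect is given the SAP's planning strength, 80% power at two-sided 0.05, which is a mean test statistic of 1.960 + 0.842 = 2.802. Under Bonferroni, power per effect is Φ(2.802 − 2.241) = 71% at 0.025 and Φ(2.802 − 2.498) = 62% at 0.0125. Simulated average power per real effect, for outcome correlations 0, 0.3 and 0.5:

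| Module | Real effects | Bonferroni | Holm |
|---|---|---|---|
| 2 outcomes | both | 71% | 77.5, 76.9, 76.5% |
| 2 outcomes | one | 71% | 71% |
| 4 outcomes | all four | 62% | 72.6, 71.7, 70.9% |
| 4 outcomes | two | 62% | 64.5, 64.3, 64.1% |
| 4 outcomes | one | 62% | 62% |

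Both methods kept module error at or below 5%. Both require the smallest p-value to be at or below 0.05/k for any rejection, so the chance of at least one rejection in a module is the same. Holm therefore leaves step 3 unchanged, apart from the correction of VRM to a 0.0125 start.

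**5. Cost of a formal gate across the 7 modules.** Holm across modules first requires a within-module adjusted p-value of at most 0.05/7. The raw threshold is 0.05/(7 × 2) = 0.0036 in a two-outcome module and 0.05/(7 × 4) = 0.0018 in a four-outcome module. An effect planned at 80% has about 46% and 37% power there.

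**The case against.** The module family is a stated choice with a stated reason, and the confirmatory effect is defined outcome by outcome. Reported as seven separate questions, 5% per module is a recognised standard. That stands, with VRM the exception. A reader might infer that the SAP treats one flagged module as proof that cognition improves. No sentence says so; the gap is that no sentence rules it out, while all the contrasts serve one research question.

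A reader might also take 20-31% as the risk of falsely claiming improvement. It counts flags for worsening too. It fits the SAP's undirected test, but the risk of a false claim of benefit is 10-17%, and both ranges rest on assumed correlations.

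A reader might see a contradiction between separate processes and correlated tasks. The documents do not support one: correlated tasks can still measure distinct processes, and difficulty in forming composites counts against treating cognition as a single construct.

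On Holm, the objection has three sound parts. Bonferroni is valid as it stands. The gain is material only when several effects in a module are real. And the results are already known, so outside VRM a switch can only add rejections, whereas the analyst-blind step was meant to guard against choices that favour significance. That governs how the change is reported; it does not remove the dominance. In VRM the change is stricter than the plan as written: a lone p-value of 0.015 passes 0.0167 but fails 0.0125.

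**Conclusion.** The point holds in limited form. Error is controlled per module, at 5% except for VRM (up to 6.7%). The VRM excess follows from the SAP's own outcome list and needs no assumption. If one flagged module were taken as a confirmatory answer to research question 1, the false-flag rate under the global null would be about 20-31% in either direction and about 10-17% toward improvement, for between-module correlations from 0.5 to 0. It would be lower if modules correlate more strongly. This is a matter of what may be concluded; it does not invalidate module-level results.

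Replacing Bonferroni by Holm is a cheap improvement at the same 5% bound. At the SAP's planning strength it adds about 6 points of average power when both of two effects are real, 9-10 points when all four are real (correlation 0.3 to 0.5), about 2 points when two of four are real, and almost nothing when one is real. It should not be offered as a remedy for the cross-module rate.

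**What to change.** (a) Use Holm within each module, counting VRM as four outcomes (first step 0.0125). Label this a post-unblinding change and show the Bonferroni results as written beside it.

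(b) State that error is controlled per module, report flagged modules as module-specific findings, and do not present one flagged module as confirmatory evidence of overall cognitive improvement.

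A Holm gate across the seven modules is optional. If used, it should require the direction of improvement, and its power cost (about 46% in two-outcome and 37% in four-outcome modules for an effect planned at 80%) should be stated.

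Cost: SAP wording and a few lines of code. Simultaneous intervals become less simple under Holm. Because the switch outside VRM can only add rejections after unblinding, the side-by-side reporting is a necessary part of the fix.

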We acknowledge that under ideal circumstances outcomes should be clearly defined along with a corresponding analysis plan prior to any data collection. We note that for this study, specific primary outcomes were defined and the analytic plan written near the end of the 5-year data collection, and for full disclosure, that 4 papers had already been published on data collected from the study.

- [name] and colleagues (2020) created a pharmacokinetic model of THC elimination using data on urine metabolites.
- [name] and colleagues (2021) examined alcohol use over the month of abstinence and the follow-up session.
- Cooke and colleagues (2021) examined anxiety and depression symptoms over the month of abstinence and the follow-up session.
- Savulich and colleagues (2021) examined sex differences over a variety of baseline characteristics, including cognitive outcomes.

Despite this order of events, the outcomes and analysis plan proposed here remain confirmatory in nature, because, in the one case that cognitive outcomes were examined, they were only examined at baseline.

Analyst-blind

To better ensure confirmatory conclusions, and to avoid unconscious bias towards adjustments that favor statistical significance, initial implementation of analyses was 'analyst-blind' (Dutilh, Sarafoglou, & Wagenmakers, 2019). In other words, analyses were first implemented on data where intervention status (whether a participant was in the CB-Abst or CB-Mon group) had been randomly shuffled. Data was shuffled by an individual outside the core ARCHES team. Only after data exclusion criteria had been determined, transformations of

predictor and outcome variables had been finalized, models had been properly specified, and any other unforeseen circumstances addressed, was the un-shuffled data provided to the analyst for the final analysis implementation.

Notable changes made during the analyst-blind period were:

- Removal of number of years spent using cannabis as a covariate. This measure was dropped due to its high correlation with a participant's overall age.
- The decision to only examine a linear trend for change over time. This decision was made due to the small number of time points (a quadratic time trend requires 3 parameters, but there were only 4 time points to estimate this trend).

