- The addition of a secondary analysis of observed data only (imputed observations were excluded). This analysis was added to assess how robust our results were to our treatment of missing data.
- The decision to model bounded count data using binomial regression rather than linear regression. This decision was implemented to better deal with non-normal and non-continuous data.
- The decision to compute standard errors and confidence intervals using the robust estimates from the GEE models rather than a combination of GEE and a bootstrap approach. This decision was implemented for computational efficiency, as the bootstrap added little beyond the robustness already provided by the GEE approach.

One additional change was made after the initial unblinded analyses were run. We incorporated a new outcome, total correct for immediate recall from the verbal recognition memory task. While this outcome is not listed as part of the recommended CANTAB measures, it was important to include based on theoretical motivations, as its inclusion allowed us to assess the replicability of the results of [name] and colleagues (2018).

Primary Outcomes

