 - a) Subjects saw an arrow pointing to the left or right. The goal of the task was to (a) indicate the direction of the arrow as quickly as possible, or (b) if a tone sounded following presentation of the arrow, avoid making a response. Subjects completed 424 trials, 318 in which they indicated the direction of the arrow (Go trials), and 106 in which the tone sounded and they were supposed to inhibit their response (Stop trials).
- 4) The Spatial Working Memory (SWM) module.
 - a) Subjects saw a set of boxes. The goal of the task was to identify via a process of elimination the box containing a hidden token. Once a token was found, a new token was hidden in a different box. Tokens were never hidden in a box that had previously had a token. Subjects completed 30 trials total. There were conditions for 4, 6, 8, and 12 boxes onscreen, with the number of trials per condition equal to the number of boxes.

Selection of outcomes

The modules listed above produce a large number of outcomes (from 10 for the SSP to 58 for the OTS). However, CANTAB provides a set of recommended outcomes for researchers, so for simplicity and consistency with established guidelines, for each module we analyzed the subset of recommended outcomes per CANTAB's manual (Cambridge Cognition, 2021). We also included one measure, total correct for immediate recall from the VRM module, which was not part of the recommended outcomes but was important to include to assess replicability of a prior study ([name] et al., 2018). Across the 7 modules, there were a total of 17 outcomes, listed below with a brief description and details on the units of measurement, range, and interpretation.

1. Outcomes to assess change in memory functioning:

1.1. The total number of errors (adjusted for number of uncompleted problems) from the **PAL** module.

- The number of times the subject chose the incorrect box for a stimulus on assessment problems plus an adjustment for the estimated number of errors they would have made on any problems/attempts/recalls they did not reach.
- Count variable, ranging from 0 to 70, where higher scores indicate more errors and worse performance.
- Data were modeled using a binomial distribution using the log-odds link function.

1.2. The first attempt memory score from the **PAL** module.

- The number of times a subject chose the correct box on their first attempt when recalling pattern locations – calculated across all trials.

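### The VRM module lists four primary outcomes but is tested at 0.05/3, and the fourth was added after unblinding while keeping confirmatory status

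*SAP*

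**What the plan says.** In the SAP under Multiple comparisons, the rule is: "we used a simple Bonferroni correction, dividing the desired error rate of 5% by the number of outcomes per module". The thresholds that follow are 0.05 for SST; 0.025 for PAL, SSP, OTS and SWM; 0.0167 for VRM; and 0.0125 for MTT.

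Under Primary Outcomes, Selection of outcomes, four VRM measures appear: immediate recall (1.5), delayed recall (1.6), immediate recognition (1.7) and delayed recognition (1.8).

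The SAP gives two counts. Primary Outcomes opens with "The 16 primary outcomes for the study were measures taken from 7 modules". Selection of outcomes says "Across the 7 modules, there were a total of 17 outcomes".

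The Analyst-blind section explains where the extra measure came from: "One additional change was made after the initial unblinded analyses were run". It goes on: "We incorporated a new outcome, total correct for immediate recall from the verbal recognition memory task". The stated reason is to check whether the pilot study's result replicates, and the SAP acknowledges that the measure is not among those CANTAB recommends. The title page dates the unblinded analysis 02/03/2023 and the last revision 04/28/2023.

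On status, the section on the order of data collection says that "the outcomes and analysis plan proposed here remain confirmatory in nature". The Key confirmatory effect section applies the abstinence-versus-monitoring contrast to every outcome, with no exception for item 1.5.

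**The concern.** There are two linked defects. The first is the divisor: a module with four listed outcomes is tested at a level that fits three, so the SAP breaks its own rule. The second is status: an outcome brought in after the un-shuffled arm data had been analysed is placed in the primary list and given a confirmatory threshold.

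The SAP's argument for calling its outcomes confirmatory is that earlier papers had looked at cognition only at baseline. That argument cannot cover a choice made after unblinded post-baseline analyses. The shuffling procedure was there to keep such choices independent of the results, and this one was made after that protection had ended.

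At stake are the significance calls for VRM and the line between pre-specified and post hoc results. Because immediate recall was added to test replication of the pilot, it may well be prominent in the report, although that is an inference. The module threshold also governs the group-by-time Wald tests in the SAP's Secondary analyses 1 and 2, so the wrong value carries into the second and third research questions.

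**Working it through.** **Inputs.** Module error rate 5% and the division rule (SAP, Multiple comparisons). Number of outcomes *k* per module, counted from the numbered list (SAP, Selection of outcomes).

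**Step 1: reproduce the thresholds, α = 0.05/*k*.**

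| Module | *k* listed | 0.05/*k* | SAP | Agrees |
|---|---|---|---|---|
| PAL | 2 | 0.025 | 0.025 | yes |
| SSP | 2 | 0.025 | 0.025 | yes |
| VRM | 4 | 0.0125 | 0.0167 | **no** |
| MTT | 4 | 0.0125 | 0.0125 | yes |
| OTS | 2 | 0.025 | 0.025 | yes |
| SST | 1 | 0.05 | 0.05 | yes |
| SWM | 2 | 0.025 | 0.025 | yes |

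The SAP's VRM figure reproduces only with *k* = 3: 0.05/3 = 0.0167. MTT, which also has four outcomes, is given 0.0125.

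**Step 2: count the outcomes.** 2 + 2 + 4 + 4 + 2 + 1 + 2 = 17. With three VRM outcomes the total is 16. The count of 16 and the threshold of 0.0167 both fit the list before immediate recall was added, so it appears that neither was updated.

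**Step 3: error rate for VRM with four tests at 0.0167.**

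- Bonferroni bound: 4 × 0.0167 = 0.0668, or 6.7%.
- If independent: 1 − (1 − 0.0167)^4 = 0.0651, or 6.5%.
- If correlated: the documents give no correlation between the VRM test statistics, so a common value ρ is assumed. With *c* the two-sided critical value for 0.0167, the rate is 1 − ∫ φ(x) [Φ((c − √ρ x)/√(1−ρ)) − Φ((−c − √ρ x)/√(1−ρ))]^4 dx.

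| ρ (assumed) | Four tests at 0.0167 |
|---|---|
| 0.3 | 6.2% |
| 0.5 | 5.7% |
| 0.6 | 5.3% |
| 0.7 | 4.8% |

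The rate reaches 5% at ρ of about 0.66.

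**Step 4: the two repairs.**

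- Four tests at 0.0125: bound 4 × 0.0125 = 5.0%; independent 1 − (1 − 0.0125)^4 = 4.9%.
- Three tests at 0.05/3: bound 5.0%; independent 1 − (1 − 0.05/3)^3 = 4.9%.

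**Step 5: power cost of the stricter level.** Take an effect with 80% power at two-sided 0.05, so its standardised shift is 1.960 + 0.842 = 2.802 (normal approximation).

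- At 0.05/3: Φ(2.802 − 2.394) = 65.8%.
- At 0.0125: Φ(2.802 − 2.498) = 61.9%.

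**The case against.** The strongest reply is that 0.0167 may be deliberate. The statement of 17 does not use the word primary, and it comes directly after the explanation that one non-recommended measure was included for replication. One could therefore read the plan as 16 primary outcomes plus one replication measure, with 0.0167 correct for the three recommended VRM outcomes. The SAP does not support this reading. Item 1.5 is listed under Primary Outcomes, the confirmatory contrast covers every outcome, and nothing places item 1.5 outside the VRM family. Even if that reading was intended, the family and the status of item 1.5 would still have to be stated.

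A second reply is that all four scores come from one 18-word list and may be strongly correlated, so the true error rate could be at or below 5%. That is possible above a correlation of about 0.66. It stands as a limit on the size of the problem, but the SAP relies on Bonferroni and claims no credit for correlation.

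Three further points stand. The addition is openly disclosed with its reason. The SAP does not say that the immediate-recall difference itself had been seen, only that unblinded analyses had been run. The loss of confirmatory status applies to immediate recall alone; the SAP reports no late change to the other three VRM outcomes. The wish to replicate the pilot predates unblinding, but the decision to include this measure does not.

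**Conclusion.** The concern holds. Under the SAP's own rule the VRM threshold for the four listed outcomes is 0.0125, not 0.0167. The 5% guarantee for the module is lost: the bound is 6.7%, and the rate is 6.5% under independence. The actual rate depends on a correlation that the documents do not give, and would be 5% or less only if that correlation exceeded about 0.66 under the equal-correlation assumption.

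The status problem does not depend on any correlation. Immediate recall was chosen after unblinded analyses, so no threshold gives it a pre-specified error rate, and its place in the confirmatory set is wrong. This should be corrected before VRM results are reported, because it affects both a primary significance rule and the boundary between pre-specified and post hoc findings.

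**What to change.** Choose one of two alternatives and state the VRM family explicitly.

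1. **Preferred.** Move immediate recall out of the primary set, label it as added after unblinding, and report it as post hoc without a confirmatory threshold. Then 0.0167 is correct for the remaining three VRM outcomes, and the count becomes 16 primary outcomes plus one post hoc.
2. **If four outcomes stay listed in the module.** Set the VRM threshold to 0.0125 and state 17 throughout. Immediate recall must still be labelled post hoc, since the stricter level repairs only the arithmetic.

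Under either alternative, qualify the statement that the outcomes remain confirmatory so that it excludes immediate recall, and apply the corrected VRM level to the group-by-time tests in Secondary analyses 1 and 2.

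The cost is SAP wording and, under the second alternative, one threshold. No new data are needed. The first alternative costs the other three VRM outcomes no power; the second lowers the illustrative power from 65.8% to 61.9%. Any VRM result with p between 0.0125 and 0.0167 should be rechecked against the alternative chosen.
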